3.1 Participants

Pediatric hemato-oncology patients (aged from 18 months to 18 years) treated for acute lymphoblastic leukemia in Helsinki, Turku, and Tampere university hospitals are eligible for the study. Informed consent is obtained from all patients and/or their parents, depending on the child's age.

The goal is to gather data from at least 150 lumbar puncture (LP) procedures of at least 50 patients and ≤ 4 procedures per patient.

3.2 Equipment

Bioimpedance spinal needle system: Injeq IQ-Tip® system

The system comprises a 22G Quincke-type spinal needle, bioimpedance analyzer and a cable for connecting the needle to the analyzer. The stylet of the needle is configured as a bioimpedance electrode. The procedure and stylet manipulation are similar with Injeq's needle and conventional spinal needle.

The equipment detects the cerebrospinal fluid (CSF) at the tip of the needle and gives clear detection alarm to the user.

3.3 Clinical procedure

Injeq's representatives gives a practical training session on the use of the equipment to principal investigators, other physicians, and research nurses before the patient recruitment begins.

All LP procedures included in the study are part of the patients' planned intrathecal treatment (IT) protocol. Lumbar punctures are performed under general anesthesia and physicians perform the procedures according to their normal schedules and otherwise normal practices.

After the CSF detection alarm, the physician removes the stylet and checks for a CSF flow through the needle. A physician can also perform the check based on his/her clinical judgement. The IT is delivered after the correct needle location is verified by the CSF flow and a CSF sample is taken for the laboratory analysis.

Study protocol & Statistical analysis plan, IQ-LP-03	Version 1
For ClinicalTrials.gov	
	Page 2 of 2

3.4 System performance assessment

After each LP procedure, the physician evaluates the system performance on a case report form (CRF). The first puncture success and accuracy of CSF detections are recorded.

First puncture success is defined as obtaining a CSF sample and/or successful IT with a single needle insertion; i.e., with one skin penetration. CSF detection sensitivity and False detection rate are defined as follows:

CSF detection sensitivity = # of correct CSF alarms / (# of correct CSF alarms + # of missing CSF alarms)

False detection rate = # of LP procedures with false alarms / # of all LP procedures

Erythrocyte count result (cells/ μ L) from the CSF sample is recorded on CRF.

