3.6 Statistical analysis

Mean, median and min-max range are reported for the descriptive data, as appropriate.

The proportion of CSF samples with ≥ 10 erythrocytes/ μ L is reported with 95 % confidence interval.

The distribution of all CSF sample erythrocyte counts is reported as a cumulative distribution curve.

The first puncture success rate is reported with 95 % confidence interval.

The CSF detection sensitivity and false detection rates are reported with 95 % confidence intervals.

Confidence intervals are calculated with the exact Clopper-Pearson method.

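### Does the 'and/or' in the definition of first puncture success make the reported rate unsound?

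*Combined protocol and SAP*

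**What the plan says.** Section 3.3 places every procedure within a treatment course: "All LP procedures included in the study are part of the patients' planned intrathecal treatment (IT) protocol". It gives the sequence at the bedside: "The IT is delivered after the correct needle location is verified by the CSF flow and a CSF sample is taken". Section 3.4 has the physician complete a case report form (CRF) after each LP: "The first puncture success and accuracy of CSF detections are recorded". It defines success as "obtaining a CSF sample and/or successful IT with a single needle insertion; i.e., with one skin penetration". Section 3.6 reports one success rate with an exact Clopper-Pearson 95% interval and does not split it into sample and IT. Section 3.1 sets the target at "at least 150 lumbar puncture (LP) procedures" from at least 50 patients, with no more than four per patient, at three university hospitals. No section states an expected success rate, a threshold or a hypothesis test for this rate.

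**The concern.** If the purpose of each LP is to give IT, a reader may take first puncture success to mean that treatment was completed through the first puncture. The definition does not require that. An LP that yields a sample through its only penetration but ends without IT counts as a success. Compared with a rule requiring IT through the same insertion, the written rule can only give an equal or higher rate.

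There is also a question of scope. The limit to one skin penetration could apply to whichever component was achieved, or to the LP as a whole. The two readings part where the sample comes at the first penetration and IT only after a second. Physicians at three hospitals score their own procedures and could settle this differently, and the single rate would not show it. What is at stake is the meaning of the reported rate: needle placement, or completed treatment at the first puncture.

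**Working it through.** The plan states no figure for this endpoint, so there is nothing to reproduce. The check has two parts: how far the wording decides each possible outcome, and how much the undecided or debatable outcomes could move the rate.

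**Outcomes under the section 3.4 definition**

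| | Sample at first penetration | IT | Scored as |
|---|---|---|---|
| A | yes | at first penetration | success |
| B | yes | never delivered | success |
| C | no | at first penetration | success |
| D | no | only after a second penetration | failure |
| E | yes | only after a second penetration | depends on the reading |

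A to D are settled by the text. Only E is open: a success if the limit applies to each component, a failure if it applies to the whole LP. B is settled, and the question there is only whether one likes the choice.

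**How likely B and E are.** Section 3.3 describes CSF flow, sampling and IT as steps through a needle already in position. Sample and IT would therefore normally share one placement, and B and E may be rare. The documents give no count.

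**Effect on the rate.** Inputs: n = 150 (section 3.1, planned minimum) and the Clopper-Pearson method (section 3.6). For x successes in n, with 0 < x < n:

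- lower limit = 2.5% quantile of Beta(x, n − x + 1)
- upper limit = 97.5% quantile of Beta(x + 1, n − x)

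One rescored LP changes the rate by 1/150 = 0.67 percentage points. The success counts and the number k of rescored LPs below are assumptions for illustration.

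| Start | k | x/150 | Rate | Exact 95% interval |
|---|---|---|---|---|
| 135 | 0 | 135 | 90.0% | 84.0 to 94.3 |
| 135 | 1 | 134 | 89.3% | 83.3 to 93.8 |
| 135 | 3 | 132 | 88.0% | 81.7 to 92.7 |
| 135 | 5 | 130 | 86.7% | 80.2 to 91.7 |
| 135 | 8 | 127 | 84.7% | 77.9 to 90.0 |
| 120 | 0 | 120 | 80.0% | 72.7 to 86.1 |
| 120 | 5 | 115 | 76.7% | 69.1 to 83.2 |

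Starting from 135, the interval reaches 90.0 − 84.0 = 6.0 points below the estimate. Rescoring five LPs shifts the estimate by 90.0 − 86.7 = 3.3 points. Even eight, a shift of 90.0 − 84.7 = 5.3 points, leaves it inside the starting interval.

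These intervals treat LPs as independent, as the plan's method does, although a patient may contribute up to four. That does not alter the 0.67-point step.

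**The case for a change.** The strongest argument for a change is that it would cost little. One sentence could fix the scope of the penetration limit, and reporting sample and IT separately would show whether placement and delivery coincide. Even a zero would be informative: with no discordant LPs in 150, the upper 95% limit is 1 − 0.025^(1/150) = 2.4%. It is also true that no written rule prevents outcome E from being scored differently between physicians. The wording points stand: a sample suffices, and E is undefined.

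The argument is weaker on consequence. Different scoring between sites is conjecture, since the CRF is not shown and may already record penetrations, sample and IT separately. Section 3.4 does place the erythrocyte result from the CSF sample on it, which largely shows whether a sample was obtained.

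The natural amendment also brings less than it seems to. Suppose two rates were reported, each requiring a single penetration for the whole LP. An LP of type E would fail both, so a listing of LPs where the two rates disagree would omit the one sequence the wording leaves open. And a rate that demands IT delivery would count against the needle any LP in which IT was withheld for a reason unrelated to placement.

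**Conclusion.** No change to the plan is called for. Accepting a CSF sample as success is a defensible endpoint for a needle whose function, described in section 3.2, is to signal CSF at its tip. Requiring IT delivery instead is a debatable preference, and it would measure something partly outside the device's control. The remaining gap is one sequence, sample first and IT after a second penetration. It is the kind of rare case an analyst resolves by stating a convention and giving the count in the report, where the records allow it.

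The size is 0.67 percentage points per affected LP at 150 LPs, so a few such LPs would move the rate by less than its own sampling uncertainty. This rests on two things. Sample and IT are assumed usually to come from one placement, as the sequence in section 3.3 suggests; the documents give no frequency. And the rate is purely descriptive: the plan sets no threshold for it, so no decision depends on how these LPs are scored. If discordant LPs proved common, the single rate should be read as a placement rate, which is what the definition makes it.

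### Does the lack of a written definition of a missing CSF alarm leave the device's sensitivity open to overstatement?

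*Combined protocol and SAP*

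**What the plan says.** Section 3.4 gives two accuracy measures for the needle system. Sensitivity is a ratio of alarm counts: "CSF detection sensitivity = # of correct CSF alarms / (# of correct CSF alarms + # of missing CSF alarms". Its companion is counted in procedures: "False detection rate = # of LP procedures with false alarms / # of all LP procedures". Neither a correct nor a missing alarm is defined further. The physician records performance on the case report form after each procedure.

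Section 3.3 describes when CSF flow is looked for. With an alarm: "After the CSF detection alarm, the physician removes the stylet and checks for a CSF flow through the needle". Without one: "A physician can also perform the check based on his/her clinical judgement". The same section adds a condition that applies whether or not the device has alarmed: "The IT is delivered after the correct needle location is verified by the CSF flow".

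Section 3.2 notes that "The stylet of the needle is configured as a bioimpedance electrode", so withdrawing the stylet to check for flow also ends detection at that position. On reporting, section 3.6 says: "The CSF detection sensitivity and false detection rates are reported with 95 % confidence intervals". The intervals are exact Clopper-Pearson. No hypothesis, target or success criterion is attached to them.

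**The concern.** The reference check looks uneven: it follows every alarm but is discretionary when the device is silent. Detecting CSF is what the device is for, so a gap in how its sensitivity is counted deserves attention. Three things could go wrong.

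1. **Hidden misses.** If the tip enters CSF, the device stays silent and nobody checks, there is nothing to record. Losing such an event from the denominator can only raise the estimate.
2. **Reclassified misses.** If the physician checks on judgement before any alarm and CSF flows, someone could argue that the electrode was withdrawn before it could respond, and set the case aside. That choice would be made with the outcome known.
3. **Mixed units.** Sensitivity counts alarms and the false detection rate counts procedures, so a puncture with several CSF entries could contribute more than once to sensitivity.

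The binomial interval would cover none of this. At stake is whether the published sensitivity means what a reader would take it to mean.

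**Working it through.** **Inputs.** Section 3.1 plans at least 150 lumbar punctures. The document gives no expected sensitivity, no number of misses and no precision target, so there is no planned figure to reproduce. Every miss count below is an assumption. Intervals are exact Clopper-Pearson, as in section 3.6.

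**Step 1: what can be seen.** All study punctures belong to planned intrathecal treatment, and section 3.3 requires CSF flow before treatment is given. A puncture completed with the study needle therefore ends in observed flow, with or without an alarm. Discretion applies only to intermediate needle positions. At the final position a silent device is evident to the person completing the form.

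**Step 2: how a visible miss is classed.** Suppose CSF is confirmed in all 150 punctures and J of them are found on a judgement check without an alarm. Counted as misses, sensitivity is (150 − J)/150. Set aside, it is (150 − J)/(150 − J).

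| J | Counted as misses | Set aside |
|---|---|---|
| 0 | 150/150 = 100% | 150/150 = 100% |
| 5 | 145/150 = 96.7% (92.4 to 98.9) | 145/145 = 100% (97.5 to 100) |
| 15 | 135/150 = 90.0% (84.0 to 94.3) | 135/135 = 100% (97.3 to 100) |

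The contrast is large only if every such case is discarded. The formula has no exclusion for early checks, and no section mentions a detection delay. CSF present with no alarm is the plain meaning of a missing alarm, so the middle column is the one the plan leads to.

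**Step 3: punctures with no alarm and no confirmed CSF.** Let U be their number, with 5 recorded misses among the rest. Confirmed CSF only gives (145 − U)/(150 − U). Counting all U as misses gives (145 − U)/150. With U = 8 these are 137/142 = 96.5% (92.0 to 98.8) and 137/150 = 91.3% (85.6 to 95.3). With U = 0 both are 145/150 = 96.7%. This is not evidence of overstatement: where the tip never reached CSF, silence is the correct response, and the puncture does not belong in the denominator.

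**Step 4: the events that could really be lost.** These are silent, unchecked passes through CSF in punctures that later succeed after a deeper advance, a later alarm or a new insertion. Take 150 punctures with CSF confirmed in all, 5 recorded misses, and 8 such passes in punctures that later alarmed. Counting the passes gives 145/(150 + 8) = 145/158 = 91.8% (86.3 to 95.5). A definition per puncture scores those 8 as correct detections and leaves 145/150 = 96.7%. Counting punctures without confirmed CSF as misses adds nothing, because there are none. Neither repair would see the loss.

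**Step 5: counting unit.** Adding 16 repeat correct alarms to 140/145 = 96.6% gives (140 + 16)/(145 + 16) = 156/161 = 96.9%, a shift of 0.3 percentage points.

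**The case for a change.** The strongest argument for acting is that seeing a miss is not the same as classifying it as one. The operating physician, who responded to the alarms, judges the device afterwards, and the plan names no independent classification. One sentence of definition would cost almost nothing, and sensitivity is a named result that readers will rely on even in a descriptive study.

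Much of this is fair. The definition is indeed unwritten, and the interval does not reflect uncertainty in classification. With J = 15 the two intervals in the table do not overlap, so a deliberate policy of discarding judgement-check cases would matter. But that policy would have to be added to the plan. The argument also does not show that a written rule would change the planned result: for judgement checks it would state what the formula already implies, and for unchecked passes it would not help. The public document runs to two pages and the case report form is not part of it, so its silence is weak evidence that the form does not record what prompted each check.

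**Conclusion.** The concern identifies missing detail but no error in a planned result. Sensitivity is reported as an estimate with an interval, and no decision rule depends on it. The requirement for CSF flow before treatment makes an alarm-free completed puncture visible, and the ordinary reading of the formula counts it as a miss. On that reading 5 such cases in 150 give 96.7%, and the rise to 100% needs an exclusion that the plan does not contain.

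Unchecked silent passes before a later success remain a genuine limit of what can be observed. Their number is unknown and may be zero; 8 of them would lower 96.7% to 91.8%, but redefining the ratio per puncture would not uncover them. The difference in counting unit is immaterial at 0.3 points in the example.

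This conclusion assumes that analysts apply the plain meaning of a missing alarm and that the form records whether an alarm preceded CSF flow. A write-up that states how misses were counted would give readers what they need.

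### Does counting a procedure once, however many false alarms it has, leave CSF detection accuracy wrongly reported?

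*Combined protocol and SAP*

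**What the plan says.** Section 3.4 states that "The first puncture success and accuracy of CSF detections are recorded" and then defines two measures of detection. The first is "CSF detection sensitivity = # of correct CSF alarms / (# of correct CSF alarms + # of missing CSF alarms"), a ratio of alarms. The second is "False detection rate = # of LP procedures with false alarms / # of all LP procedures", in which each LP is scored yes or no.

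Section 3.6 takes up the same two: "The CSF detection sensitivity and false detection rates are reported with 95 % confidence intervals". It adds that "Confidence intervals are calculated with the exact Clopper-Pearson method".

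Two other places bear on the point. In section 3.3, "After the CSF detection alarm, the physician removes the stylet and checks for a CSF flow through the needle"; the same section lets the physician check on clinical judgement as well, and CSF flow confirms the needle's position before the intrathecal treatment is given. Section 3.1 aims for "at least 150 lumbar puncture (LP) procedures of at least 50 patients", with no more than four LPs per patient.

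**The concern.** In a study of a device alarm, a reader may want to know how often an alarm is right. The planned rate does not change when false alarms repeat within one LP, and sensitivity uses only correct and missing alarms. Neither output reacts to repeats.

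The two measures also use different units: sensitivity counts alarms, and the false detection rate counts procedures. It can look as if section 3.4 sets out to capture accuracy and section 3.6 then leaves half of it out.

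An alarm prompts the physician to withdraw the stylet and look for flow. An alarm that went off falsely several times in a few LPs would therefore mean extra checks that the planned rate does not show. If the case report form (CRF) asks only whether there was any false alarm, the counts could not be recovered later.

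**Working it through.** **Inputs from the documents.** The two definitions (section 3.4), the two planned outputs and the Clopper-Pearson method (section 3.6), and the target of 150 LPs (section 3.1). The documents give no expected rate and no frequency of repeat alarms, so there is no figure of the plan's own to reproduce. All alarm counts below are assumptions.

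**Algebra.** Let TP be correct alarms, FN missing alarms, FP false alarms, L the LPs with at least one false alarm, N all LPs, and m the mean number of false alarms per affected LP, so that FP = L × m.

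- Sensitivity = TP / (TP + FN)
- False detection rate = L / N
- PPV = TP / (TP + FP) = TP / (TP + L × m)

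Neither planned output contains m. Because FP ≥ L, the raw counts give an upper bound for PPV, TP / (TP + L). The bound is exact when no LP has more than one false alarm.

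**Illustration.** Assume N = 150, TP = 140, L = 15. The planned rate is 15/150 = 10.0% (Clopper-Pearson 5.7 to 16.0) in every row.

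| False alarms in the 15 affected LPs | FP | PPV | False alarms per 100 LPs |
|---|---|---|---|
| one each | 15 | 140/155 = 90.3% | 10 |
| 10 with one, 4 with two, 1 with three | 21 | 140/161 = 87.0% | 14 |
| two each | 30 | 140/170 = 82.4% | 20 |
| three each | 45 | 140/185 = 75.7% | 30 |

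With other values of L, still with TP = 140, the share of alarms that are false for one, two or three per affected LP is:

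- L = 5 (planned rate 3.3%, 1.1 to 7.6): 5/145 = 3.4%, 10/150 = 6.7%, 15/155 = 9.7%.
- L = 30 (planned rate 20.0%, 13.9 to 27.3): 30/170 = 17.6%, 60/200 = 30.0%, 90/230 = 39.1%.

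The large gaps need every affected LP to have two or three false alarms. In the mixed row the false share is 21/161 = 13.0%, against 15/155 = 9.7% with no repeats: 3.3 percentage points.

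**What the text commits to.** Section 3.4 names accuracy of detection and at once says how it is measured. Section 3.6 reports those measures and no others. The two sections agree, and both measures can be computed from their definitions. The different units do no harm, because each ratio has its own stated denominator and the plan never combines the two. Section 3.3 describes what follows an alarm but does not say that an LP can have several false ones.

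**Fit with the interval method.** The per-LP rate gives one yes/no result per LP, which is the form Clopper-Pearson needs at LP level. An alarm-level share would fit less well. Assume that 14 of the 15 affected LPs also had a correct alarm. With three false alarms each, Clopper-Pearson for PPV gives 68.8 to 81.7, against 67.3 to 85.2 when whole LPs are resampled, and the variance is 2.1 times the binomial one. In the mixed case the intervals nearly coincide (80.8 to 91.7 against 80.8 to 92.8; variance ratio about 1.4). Several LPs per patient is a separate matter that affects every proportion in section 3.6; it is not settled here.

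**The case for a change.** The strongest argument for the concern is that PPV is what the physician needs at the moment of the alarm, that nothing planned supplies it, and that counting false alarms would cost little. The sentence in section 3.6 on means, medians and ranges for descriptive data does not name alarm counts, so it cannot be relied on to fill the gap. Naming PPV now would also avoid choosing it after the results are seen.

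The algebra in this argument stands. If false alarms repeat, PPV cannot be derived from the planned outputs. It is also true that the public text does not say whether the CRF counts each false alarm; the form is not shown, so the counts may or may not be collected.

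The step from there to a fault does not stand. A trial need not report every measure that its data could support, and the documents never offer an alarm-level share. Counting is also less simple than it sounds: someone would have to say what makes two alarms separate, for instance when the device sounds again at the same needle position. The existing yes/no item avoids that question. Nor would the count measure the burden of extra checks, since physicians may also check without an alarm. Finally, a bootstrap interval for PPV would have no width if no false alarm occurred, so an alternative would have to be named in advance.

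**Conclusion.** The concern does not hold. The per-LP false detection rate is a valid proportion with a clear numerator and denominator. Section 3.6 reports what section 3.4 defines, and the plan followed as written answers its stated questions. PPV would be an additional output that some readers might like; its absence is not an error.

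The size of what goes unreported is unknown. Under the assumed 150 LPs, 140 correct alarms and 15 affected LPs, PPV is 90.3% without repeats, 87.0% in the mixed case and 75.7% with three false alarms in every affected LP. Without repeats nothing is lost, because the raw counts give PPV. The documents give no reason to prefer any of these cases. The conclusion rests on reading the two definitions in section 3.4 as the plan's full account of detection accuracy, which is how section 3.6 uses them.
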